**Protocol Title: A Prospective Controlled Treatment Trial for Post-Traumatic Headaches**

**NCT#: 03007420**

**Principal Investigator: [name]**

**A. SPECIFIC AIMS AND HYPOTHESIS**

**1. To compare the efficacy of Occipital Nerve Blocks (ONB) vs. Cervical Medial Branch Blocks (CMBB) in patients presenting with post-traumatic headache (PTH) who were non-responsive to previous interventional management.**

- To examine differences in Numeric Rating Scale (NRS) pain measurements (> 50% or < 50% pain reduction)
- To examine differences in Migraine Disability Assessment (MIDAS) and Pediatric Migraine Disability Assessment (PedMIDAS) scores
- To describe differences in functional outcomes using the Functional Disability Inventory (FDI) and the Pain Disability Index (PDI).
- To study differences in Quality of Life (QL) and Pediatric Quality of Life (PedsQL) scores

**Hypothesis:** Treatment with CMBB with steroids and lidocaine will be associated with a greater improvement in pain scores, functional and QL scores than the ONB.

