**2. To describe the baseline socio-demographic characteristics of individuals with PTH and chronic axial neck pain.**

- To study gender, BMI, age, school and work absences and disrupted sleep
- To study psychological (anxiety, depression) and pain related comorbidities (whole body pain, gastrointestinal problems, small fiber neuropathy)
- To study correlation to nature of injury (concussion vs. head injury and severity of injury based on 1997 AAN guidelines)
- To study previous treatment methods and interventions

**Hypothesis:** Of the participants with PTH, the majority will exhibit school or work absences and disrupted sleep. The majority of participants will also have higher scores of anxiety and depression, more pain related comorbidities, history of prior injury, and previous treatment from other providers.

**3. To describe and understand how clinical features, physical exam characteristics, and radiologic findings among patients with PTH and axial neck pain associate with treatment response for each of the treatment options.**

- To assess physical exam characteristics (axial neck pain which is extension related, myofascial spasms and occipital neuralgia)
- To characterize the diagnosis given by the clinicians in their notes
- To characterize the presence of radiologic or predictive clinical findings such as facet arthropathy, disc changes, spondylolysis, or spondylolisthesis

**Hypothesis:** Treatment response (improvement in pain) will be associated with features on the physical exam (neck pain with extension, headaches associated with cervicogenic causes) and with presumed anatomic diagnosis (facet arthropathy, spondyloysis, spondylolisthesis, axial and discogenic pain).

**4. To study the effects of socio-demographic, clinical, and psychosocial predictor variables on CMBB and ONB treatment outcomes.**

**Hypothesis:** The likelihood of improvement with CMBB or ONB is associated with a combination of socio-demographic, clinical/anatomic, and psychosocial variables. Improved responses following treatment with ONB and CMBB will be associated with a shorter duration of pain prior to intervention, normal weight, younger age and lack psychological comorbidities.

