**3. Description of Study Treatments or Exposures/Predictors**

Patients enrolled in the study will be randomized to receive either an ONB (Figure 2, additional procedure details provided below) with dexamethasone 2mg each site with 3ml 1% lidocaine, for a total of two sites or a CMBB (Figure 3a & 3b, additional procedure details provided below) with dexamethasone 1.5mg each site with 2 ml 1% lidocaine, for a total of three sites on each side. The assignment of the procedure will be randomized however neither the patients nor the investigator will be blinded to the procedure. If patients exhibit a  $\geq 50\%$  pain reduction on receiving the block evaluated after four weeks, then they may continue to receive blocks as needed, but not more than one every three months. If patients exhibit  $< 50\%$  pain reduction, the patient will be treated as per the clinician's judgment with the possibility of a cross over to the other treatment option in the protocol.

All patients will be followed for 12 months after enrollment and after the crossover of treatments they will continue to be treated and followed per clinical standard of care.

As part of this study, patients will need to complete 8 follow-up visits, of which the first and second will be in-person clinical visits and the other follow-ups could either be conducted in-person at the clinic or via teleconference - video:

a) Visit 1: in-person clinic visit

- At the first visit to the clinic, the physician or nurse will verify the patient's name and date of birth, and will collect information about pain, current and past medicines, and general health. The physician will perform a physical examination and measure heart rate, blood pressure and respiratory rate, and conduct a neurological exam.
- Baseline questionnaires will be taken, including Pain (NRS), Concussion Symptom Score, MIDAS/PedMIDAS, Anxiety, Depression, FDI, and QL.

At the end of the visit, all enrolled patients will be randomized to one of the two minimally invasive procedures, the ONB or the CMBB. Information from the patient's most recent clinical visit note (retrieved from the patient's medical record) may be used to obtain Visit 1 data.

b) Visit 2: Cervical and medial branch block procedures

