## **I. Data Analysis Plan and Sample Size**

At the time of data analysis, datasets will be downloaded from both REDCap and InForm and merged into Statistical Analysis Systems 9.3 for purposes of analysis. Missing data will be accounted for when the data is coded into respective variables.

In order to detect a 30% difference between treatment groups, and with an  $\alpha$  of 0.05 and  $\beta$  of 0.8, we will need a sample size of 24 subjects per group. Taking into consideration a 30% dropout rate during the study, we estimate a sample size of 63 subjects in the trial.

We will analyze pain scores (NRS), MIDAS/ PedMIDAS, FDI and QL scores as continuous variables. Differences of these parameters from baseline will be the outcomes variables. The differences in pain, functional, and QL scores will first be tested for normality. Assuming normality, T-Tests will be conducted to investigate the differences between the two randomized

groups. If data does not appear to be normal, Wilcoxon Rank Sum Tests will be performed in contrast to T-Tests.

Descriptive statistics will be generated in order to summarize socio-demographic characteristics of study participants. Frequency tables will be generated to describe gender, psychological and pain related comorbidities, history of injury, previous treatment methods and interventions. Similarly, frequency tables will be generated to depict physical exam characteristics, presumed anatomic diagnosis provided by clinicians, and presence of any predictive clinical findings. Continuous characteristics such as age and BMI will be tested for normality using the Shapiro-Wilk test. Continuous characteristics will be summarized using mean and standard deviation if the distribution appears normal, or will be summarized using median and interquartile range if the distribution does not appear normal. We will evaluate baseline differences between responders and non-responders, using chi-square and t-test for categorical and continuous variables, respectively.

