Additionally, pain, functional, and QL scores will be assessed at multiple time points after treatment. Repeated measure analysis will be used to compare the pain, functional and QL scores over time between groups and compared with baseline values. We will also use multiple regression analysis where treatment, epidemiological, clinical, and psychosocial characteristics will be used as independent variables. Exploratory analysis comparing the two interventional groups will also be performed in order to generate future hypothesis of the best sequential treatment algorithm in PTH.

The fluoroscopy time and radiation exposure amount will be checked for normality using the Shapiro-Wilk Test. If data is assumed to be normal, an analysis of variance will be conducted to assess difference in mean fluoroscopy time and radiation exposure amount. If data does not appear normal, a Kruskal-Wallis test will be performed.

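### For Aims 3 and 4, the only feature-by-feature test spelled out compares responders with non-responders, which loses at least about 36% of the information if NRS change is roughly normal

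*Combined protocol and SAP*

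**What the plan says.** Section I sets the scale of the outcome: "We will analyze pain scores (NRS), MIDAS/ PedMIDAS, FDI and QL scores as continuous variables", and then "Differences of these parameters from baseline will be the outcomes variables". In the same section, at the end of the paragraph on descriptive statistics, it plans the comparison at issue: "We will evaluate baseline differences between responders and non-responders, using chi-square and t-test for categorical and continuous variables, respectively".

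Section I does not say what a responder is, or when response is judged. Two other places give a 50% cut-off. Aim 1 in Section A reads "To examine differences in Numeric Rating Scale (NRS) pain measurements (> 50% or < 50% pain reduction", with no time point and with exactly 50% left in neither class. Section D.3 puts a reduction of 50% or more in the favourable class and refers to "pain reduction on receiving the block evaluated after four weeks, then they may continue to receive blocks as needed". The two differ at exactly 50%.

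Aim 3's hypothesis is worded in terms of improvement: "Treatment response (improvement in pain) will be associated with features on the physical exam". Aim 4's hypothesis is worded in terms of the chance of improving. Section I also adds: "We will also use multiple regression analysis where treatment, epidemiological, clinical, and psychosocial characteristics will be used as independent variables". That sentence names no dependent variable, time point or model-building method, and nothing says whether it or the responder comparison leads for Aims 3 and 4.

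**The concern.** Aims 3 and 4 succeed only if features truly associated with improvement can be detected. Reducing a 0-to-10 pain change to two classes before testing discards how much each patient improved. From a baseline of 9, a fall to 5 (4/9 = 44%) and a fall to 4 (5/9 = 56%) land in opposite classes although they differ by one point, while a fall to 4 and a fall to 0 count the same. The comparison is also unadjusted for baseline NRS.

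In a trial of this size the cost is a higher chance of reporting that a real predictor has no association. Because the regression's outcome and the order of the two analyses are open, the lead predictor result could also be chosen after the data are seen.

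**Working it through.** **Inputs from the documents.** The evaluable target is 24 per group, so 2 × 24 = 48. Enrolment is 63, and with the stated 30% dropout 63 × 0.7 ≈ 44 remain. Alpha is 0.05, taken here as two-sided because the plan does not say. The plan gives no power figure for the predictor analyses, so there is none to reproduce. Its sample size statement ("In order to detect a 30% difference between treatment groups, and with an" α of 0.05) concerns the comparison of arms.

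**Assumptions, not in the documents.** Change in NRS is approximately normal; the share of responders is 50%, 30% or 20%; the true correlation between a continuous feature and NRS change is 0.3 or 0.4.

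**Step 1: information kept by the split.** For a normal outcome cut so that a share p respond, efficiency relative to the continuous outcome is φ(z_p)² / [p(1 − p)].

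- p = 0.5: 0.3989² / 0.25 = 0.637, a loss of 36%. This is the smallest loss at any cut. Equivalent N: 48 × 0.637 = 30.6.
- p = 0.3 or 0.7: 0.3477² / 0.21 = 0.576, a loss of 42%. Equivalent N: 27.6.
- p = 0.2 or 0.8: 0.2800² / 0.16 = 0.490, a loss of 51%. Equivalent N: 23.5.

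**Step 2: power for one feature.** Simulation with 40,000 replicates per case, testing the feature against continuous change and then by t-test between responders and non-responders:

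| N | Correlation | Continuous change | Split 50:50 | Split 30:70 | Split 20:80 |
|---|---|---|---|---|---|
| 48 | 0.4 | 82% | 62% | 57% | 50% |
| 48 | 0.3 | 56% | 38% | 35% | 30% |
| 44 | 0.4 | 78% | 58% | 53% | 46% |
| 44 | 0.3 | 52% | 35% | 32% | 27% |

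Hand check at N = 48 and correlation 0.4, using power ≈ Φ(atanh(r)·√(N − 3) − 1.96):

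- Continuous: atanh(0.4) × √45 = 0.4236 × 6.708 = 2.84, so Φ(0.88) ≈ 81%.
- Split 50:50: the correlation shrinks to 0.4 × √0.637 = 0.319, atanh = 0.331, 0.331 × 6.708 = 2.22, so Φ(0.26) ≈ 60%.

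Both agree with the simulation to within about two points. A larger N does not remove the gap: with all 63 patients and correlation 0.4, power is 91% against 74% or 70%. Within one arm of 24, which matters because Aim 3 asks about each treatment option, it is 50% against 34% or 31%.

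**Step 3: does the loss survive a more realistic NRS?** Whole-number scores were simulated with mean baseline 6.5 and mean fall of 2 or 3 points, then classified by a 50% relative reduction. About 34% and 50% responded. The loss was 44% and 39% against absolute change, and 40% and 33% against percentage change.

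**Step 4: when is the loss small?** If change comes from two separated groups and the feature acts on group membership, the loss is 25% at a separation of 1 SD, 6% at 2 SD, and absent at 3 SD or more.

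**Step 5: can the regression stand in?** Counting model terms from the list of other independent variables in Section E: age, BMI and sex (3); headache type in four classes (3); neck pain pattern in three classes (2); symptom duration (1); concussion score (1); anxiety and depression (2); four pain comorbidities (4); seven anatomic diagnoses, if exclusive (6); and treatment (1). The sum is 23, and 48 / 23 ≈ 2 patients per term. A joint fit of that size would be unstable.

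**The case against.** The strongest reply is that the plan already holds a continuous predictor analysis. Section I makes change from baseline the outcome variable and then plans a multiple regression on treatment, epidemiological, clinical and psychosocial characteristics, which closely matches Aim 4. A reader might infer from the responder sentence that splitting is the plan's only test of predictors, and that a third of the information is therefore lost to the trial. The documents do not support that. Read together, the sentences most naturally mean a regression on continuous change, and the plan does not say that all features enter at once. What remains is that the regression's outcome, time point and rank are unstated.

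Second, a responder comparison answers a question that the protocol asks: Aim 1 uses a 50% reduction, Aim 4 speaks of the chance of improving, and Section D.3 uses the same threshold for later treatment. That stands, and is a reason to keep the comparison, though not to let it lead the search for predictors.

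Third, the 50% cut is relative while the planned outcome is a difference. A fall from 4 to 2 meets 50%; a larger fall from 9 to 5 does not. So Steps 1 and 2, which cut a single normal variable, are approximate. Step 3 applies a relative cut and gives a similar loss.

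Fourth, normality and the correlations are assumed, and Section I itself allows for non-normal data. This is correct and is carried into the verdict.

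**Conclusion.** The point holds for the responder comparison, not for the plan as a whole. If NRS change is roughly normal, that comparison loses at least about 36% of the information on each feature, and 42% at a 30:70 split. With 48 evaluable patients, power falls from about 82% to 62% or 57% for a correlation of 0.4, and from about 56% to 38% or 35% for 0.3. The percentage loss does not depend on the sample size. It does depend on the shape of the distribution, and would be small or absent with strongly bimodal change; the documents give no evidence on that shape.

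The multiple regression probably recovers part of this, but the text does not secure it. These aims lie outside the randomised comparison, whose tests already use continuous change, so the efficacy comparison is not affected.

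**What to change.** In Section I:

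- Make the lead predictor analysis for Aims 3 and 4 a linear model of NRS change at a stated time point on each baseline feature, adjusted for baseline NRS.
- State that the multiple regression uses the same outcome at the same time point.
- Keep the responder versus non-responder comparison as a secondary, descriptive summary. Define responder and its time point there, after reconciling the cut-offs in Aim 1 and Section D.3, which differ at exactly 50%.

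The cost is SAP wording; no new data are needed. The small downside is that the contrast most familiar to clinicians is no longer the lead inferential result, although it is still reported.

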#### **J. Adverse Event Criteria and Reporting Procedures**

Adverse or unanticipated events will be reported as required to the Boston Children's Hospital and other site IRB's according to institutional reporting requirements. An adverse event log will be used to document adverse events.

An Adverse Event (AE) refers to any untoward medical occurrence associated with the use of Amitriptyline, whether or not considered drug related, as described in 21 CFR 312.32. We will monitor and report any AEs, as guided in 21 CFR 312.32.

The intensity (grade) of each AE will be assessed using the following scale:

- i. Grade 1 (Mild): Experiences which are usually transient, requiring no special treatment, and do not interfere with the subject's daily activities.
- ii. Grade 2 (Moderate): Experiences which introduce some level of inconvenience or concern the subject, and may somewhat interfere with daily activities, but are usually ameliorated by simple therapeutic measures (may include drug therapy).
- iii. Grade 3 (Severe): Experiences which are unacceptable or intolerable, significantly interrupt the subject's usual daily activity, and require systemic drug therapy or other treatment.
- iv. Grade 4 (Life-threatening): Experiences which cause the subject to be in imminent danger of death.
- v. Grade 5 (Death): Subject fatality

If the intensity (grade) changes within a day, the maximum intensity (grade) should be recorded. If the intensity (grade) changes over a longer period of time, the changes should be recorded as separate events (having separate onset and stop dates for each grade).

Relationship to the medication or procedure administration will be determined by the Investigator according to the following criteria:

- i. Unexpected/Expected Adverse Drug Events
  - a. Unexpected: Any adverse experience, the nature, severity or frequency of which is not consistent with the risk information described in the investigational plan or protocol or consent form. Unexpected refers to an experience that has not been previously observed. This includes events that are more serious than expected or occur more frequently than expected.
  - b. Expected: Those experiences that have been identified in nature, severity, or frequency in the current investigator brochure, investigational plan/protocol and current consent form.
- ii. Relatedness
  - a. Unrelated: The adverse event is clearly not related to the investigational agent
  - b. Unlikely: The adverse event is doubtfully related to the investigational agent
  - c. Possible: The adverse event may be related to the agent

- d. Probable: The adverse event is likely related to the investigational agent
- e. Definite: The adverse event is clearly related to the investigational agent

For the purpose of safety analyses, all AEs that are classified as possible, probable or definite will be considered treatment-related events.

We regard the following as AEs for ONB and CMBB procedures:

- Neurotoxicity: The injection of anesthetics or steroids, or meningeal inflammation from the breech of the spinal canal during the procedure with or without direct neural injury can result in arachnoiditis or cauda equina syndrome. We regard these risks to be extremely low.
- Neurological injury: Direct mechanical injury to the spinal nerves or the spinal cord itself can occur during needle placement for injections. We regard these risks to be extremely low.
- Vascular injury: Unintentional vascular injection of the steroid and local anesthetic suspension will result in medications simply being carried away from the site of inflammation, thus reducing any local anti-inflammatory effect. In contrast, intra-arterial injection is far less common, but may cause catastrophic neurologic injury and seizures. We regard these risks to be extremely low.
- Pharmacologic effects of corticosteroids: The administration of exogenous corticosteroids can lead to both hypercortisolism and suppression of the adrenal cortex's normal production of endogenous glucocorticoids. The long-acting corticosteroid preparations used for injections slowly release the active steroid over 1 to 3 weeks. Fluid retention, weight gain, increased blood pressure and cushingoid side effects have been reported. Glucocorticoid administration reduces the effect of insulin and results in increased blood glucose levels and insulin requirements in diabetics for 48 to 72 hours. Although rare, allergic reaction to systemic administration of corticosteroid has also been documented. We regard these risks to be extremely low.
- Bleeding complications: Injections for pain treatment carries the risk of bleeding in patients without any apparent coagulopathy. Significant bleeding can cause compression of surrounding structures, potentially resulting neurological problems and worsening pain. We regard these risks to be extremely low.

- Infectious complications: Injection therapy for pain treatment carries a small risk of both superficial and deep infection, including neuraxial complications including sensory and motor deficits. Other complications include osteomyelitis and septic arthritis of the facet joints. We regard these risks to be extremely low.

In order to safeguard the privacy of patients, we have developed a mechanism for data and safety monitoring. A Data and Safety Monitoring Board (DSMB) will be established and will consist of 2 members (see DSMB Plan and Charter). The PI will not be members of this board. All members of the DSMB will pay special attention to occurrence of AEs and SAEs.

Reporting to the DSMB will occur if any 1 subject experiences a SAE as identified by the PI.

Data and safety monitoring will be performed once per year by the DSMB.

No individual care data will be reported unless there is a serious adverse effect. Reports will be done in an aggregated way.

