**5. To study the safety of the ONB and CMBB treatment.**

- To study fluoroscopy time and amount of radiation exposure
- To study sedation method if any including the use of propofol, benzodiazepine or fentanyl vs. awake procedure
- To study anesthetic complications

**Hypothesis:** The time of fluoroscopy and radiation exposure will be low, and anesthetic complications or side effects will be minimal.

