The patient will be placed in the prone position in the procedure room on a Steris table with fluoroscopy. The back of the neck will be prepped and draped in the usual sterile fashion with ChloraPrep. Under fluoroscopy guidance the high cervical facets will be visualized in AP, oblique and lateral views. Using a 22-gauge, 2-1/2-inch spinal needle, the left C 4-5 facet joint/medial branch area will be accessed under fluoroscopy. 1% lidocaine will be used for the skin and subcutaneous analgesia. Contrast omnipaque 300 mg/ ml, 0.5 ml will be used to confirm the needle position. Similar procedures will be repeated at C2-3 and C 3-4 levels. Similar procedures will be done on the corresponding levels on the contralateral side. Dexamethasone 1.5 mg with 2 mL of 1% lidocaine will be injected at each of these levels. A maximum of 9 mg of dexamethasone will be used. The patient will be observed in recovery for complications of bleeding, worsening of symptoms or paresthesias.

After the procedure is completed, all patients will recover in the Post Anesthesia Care Unit (PACU). Patients will be examined and they will be required to complete questionnaires. Patients will be discharged from the hospital per hospital guidelines and standard of clinical practice.

c) Visit 3 to 8: in-person visit or tele-conference

At 1, 2, 3, 6, 9, and 12 months after enrollment, patients will be evaluated to determine how well they did after the procedures. This would include the same steps from previous appointments. If the study treatment has been helpful, the physician might decide to continue the treatment with the procedures as needed. Clinical criteria and patient – physician agreement would be used to determine next steps in the patient's treatment plan.

d) E-mail questionnaires:

During the first two months of the study, patients will be contacted by our research team via email on a weekly basis requesting them to complete a short questionnaire that includes questions about their pain scores (NRS), MIDAS/ PedMIDAS, QL, FDI, Anxiety, Depression, and Concussion Symptoms Score. After the initial 2 months on the study, we will continue to contact patients every 2 weeks over the next 10-months (follow-ups over a total of 12 months). See Table 1 below for REDCap survey schedule.

[figure not shown]
Table 1: Schedule of REDCap surveys

Follow-Up	Questionnaire
Week 0	Migraine disability
	Pain Assessment
	Concussion Score
	General functionality
	Quality of Life
	Anxiety
	Depression

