## **L. Risks and Discomforts**

The study treatments are part of the clinical standard of care for this patient population. Some patients may experience known drug side effects, or pain, bruising and anxiety from treatment. However, we expect the risks to be minimal. Patients will be removed from the study at any point if the attending physician feels that treatment may be inappropriate to that patient's care at that time or they develop any unexpected complications. The patient will be treated for any potential reactions. If a patient enrolled in the study should have an adverse event not typically associated with the study drug and the reaction is severe or life-threatening, then the investigator or the attending physician may choose to withdraw the patient from the study. If this occurs, the patient will be withdrawn and unblinded and the IRB notified of the occurrence.

For the interventional procedures such as the nerve block injections, the patient may receive sedation per physician's discretion. If the patient requires sedation for the procedure we will inject drugs into the bloodstream generally using the intravenous route. We aim to reduce anxiety and pain, and achieve partial or total amnesia. The risks associated with sedation are an unconscious state, depressed breathing, and injury to blood vessels. We regard the likelihood of any side effects occurring from this procedure to be extremely low.

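### The general adverse-event definition names amitriptyline, which neither arm is assigned, and Section L does not separate stopping treatment from leaving follow-up

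*Combined protocol and SAP*

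**What the plan says.** **Adverse-event definition.** Section J gives one general definition: "any untoward medical occurrence associated with the use of Amitriptyline, whether or not considered drug related". Section D.3 describes the treatments: "Patients enrolled in the study will be randomized to receive either an ONB" or a CMBB, both with dexamethasone and 1% lidocaine.

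Section J has two further provisions that do reach the procedures. The lead-in to causality reads "Relationship to the medication or procedure administration will be determined by the Investigator according to the following criteria", although the grades beneath it speak of an agent, for example "The adverse event is likely related to the investigational agent". A list of six categories then opens with "We regard the following as AEs for ONB and CMBB procedures".

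**Contrast and sedation.** For the CMBB, Section D.3 states: "Contrast omnipaque 300 mg/ ml, 0.5 ml will be used to confirm the needle position". No contrast is described for the ONB. Sedation is planned for pediatric patients and some very anxious adults. Section L says of it: "The risks associated with sedation are an unconscious state, depressed breathing, and injury to blood vessels". Aim 5 includes the objective "To study anesthetic complications".

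**Removal.** Section L makes removal from the study obligatory if the attending physician judges that treatment may be inappropriate, or if the patient has any unexpected complication. Shortly afterwards it makes withdrawal optional for a severe or life-threatening event that is not typical of the study drug, and says that a withdrawn patient is unblinded. Section D.3 has all patients followed for 12 months after enrollment. Section D.1 has them in the study for at most 12 months.

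**The concern.** A general adverse-event definition is the rule that should catch whatever a specific list leaves out. Here it is tied to a drug that is not a study treatment. The definition is in use: the adverse-event log, the classification of events as treatment-related for the safety analyses, and the monitoring board's review all depend on what counts as an adverse event. Aim 5 predicts that anesthetic complications or side effects will be minimal. A low count is easier to trust if the definition fits the two blocks, the contrast and the sedation.

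The removal rule raises a separate question. The complication itself comes before removal and can be logged. If removal also ends data collection, its course and resolution go unrecorded, and so do that patient's later scores on the numeric rating scale (NRS), the primary outcome. Those data would be missing because of something that happened after randomization and was related to treatment. Section I has only one unspecific sentence on missing data.

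**Working it through.** The plan gives no figure of its own on this point. The check is a comparison of texts, followed by a count from Table 1.

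**1. Definition against treatments.** Arms assigned amitriptyline: 0 of 2. The drug otherwise appears only in Section B, in the account of an outside trial.

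**2. What the list covers.** The six categories are neurotoxicity, neurological injury, vascular injury, corticosteroid effects, bleeding and infection.
- Contrast: no category names it. The only allergic reaction listed is to corticosteroid. Because contrast is described only for the CMBB, this gap falls on one arm.
- Sedation: Section L names three risks, and none is carried into the list as a sedation event. Vessel injury resembles the vascular category in name, but that category describes steroid and local anesthetic entering a vessel.

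**3. Relatedness.** There are five grades. Four refer to the investigational agent and one to the agent. The lead-in brings the procedure into scope, but the grades do not follow it. Mechanical needle injury, which is on the list, fits the lead-in and not the grades.

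**4. Removal against follow-up.** D.3 states follow-up for all without exception, D.1 states a maximum, and L states obligatory removal. None says whether surveys, visits or adverse-event follow-up continue after removal.

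**5. What could be lost per removed patient.** Table 1 has 8 post-baseline surveys up to the 2-month evaluation, 2 more to 3 months, and 6 in each of the next three quarters: 8 + 2 + 6 + 6 + 6 = 28. Each includes pain and side effects. Visits 3 to 8 give 6 visits. The counts below assume that removal ends data collection. The first row also assumes that the first block comes before the Week 1 survey. The protocol states neither.

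| Removed after | Surveys lost | Visits lost |
|---|---|---|
| first block | 28 | 6 |
| 1-month evaluation | 28 − 4 = 24 | 6 − 1 = 5 |
| 3-month evaluation | 28 − 10 = 18 | 6 − 3 = 3 |
| 6-month evaluation | 28 − 16 = 12 | 6 − 4 = 2 |
| 9-month evaluation | 28 − 22 = 6 | 6 − 5 = 1 |

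The later rows are possible because D.3 allows crossover after the four-week evaluation and repeat blocks at intervals of at least three months.

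**6. Scale.** No removal rate is given and none is assumed. For scale only, 1, 2 or 3 patients are 1/63 = 1.6%, 2/63 = 3.2% or 3/63 = 4.8% of the planned sample. The dropout already allowed for is 0.30 × 63 = 18.9, about 19 patients.

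**The case against.** **On the definition.** The amitriptyline wording is plainly a leftover, and the rest of the plan works around it. Section J opens by requiring adverse or unanticipated events to be reported to the ethics boards, before the faulty definition appears. It expressly counts six categories as adverse events for the two procedures. Every post-baseline survey asks about side effects of the invasive treatment. A separate anesthesia team checks vital signs every 5 minutes, and patients are examined in recovery. Repeating the sedation risks in the list could be called drafting preference. All of this is correct and limits the harm. It does not repair the one general definition, which remains wrong for unlisted events. Contrast is the clearest example.

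**On removal.** A general follow-up schedule alongside a withdrawal provision is not in itself a contradiction. D.1 makes 12 months a maximum, and Section I allows for dropout. The contrast between obligatory and optional withdrawal leans on a sentence about a study drug and unblinding, which is itself leftover text in a trial where nobody is blinded. If Section L uses *unexpected* in the sense of Section J, the trigger is narrow, because events consistent with the risks already described do not count. These objections stand. What survives them is that Section L treats stopping treatment and leaving follow-up as one act.

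**On unseen material.** The adverse-event log, the consent form and the monitoring board's charter are not available here. They may say more about contrast or about follow-up after removal.

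**Conclusion.** Both defects are real, limited and worth correcting. The general adverse-event definition names a drug that 0 of 2 arms is assigned, which leaves events outside the six listed categories without a fitting definition. Section L does not separate stopping treatment from leaving follow-up. If removal ends data collection, later safety and NRS data are lost for a treatment-related reason, at most 28 surveys and 6 visits per removed patient under the assumptions stated with the table.

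A reader might infer more, and the documents do not support it:
- *That an event after a block counts only if it is associated with amitriptyline.* The six-category list is a second, express inclusion.
- *That events have been or will be missed.* No lost event is shown, and several other routes of capture are in place.
- *That Section L flatly contradicts 12-month follow-up.* D.1 allows less than 12 months, and the protocol does not say that data collection stops on removal.
- *That the primary comparison is seriously biased.* The number of removals is unknown. It is probably small, since the plan calls each listed risk extremely low, and a few removals would add little to about 19 planned dropouts.

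The consequence falls mainly on the adverse-event and anesthetic-complication part of Aim 5. The fluoroscopy and radiation part has its own stated analysis and is not affected.

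**What to change.** **Section J.** Define an adverse event as any untoward medical occurrence from the first study procedure onward, in either arm, whether or not considered related to the block, injectate, contrast or sedation. Use the same terms in the five relatedness grades in place of the agent wording. Carry the three sedation risks from Section L into the list, and add contrast reactions for the CMBB.

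**Section L.** Replace removal or withdrawal from the study with stopping study treatment, in both the obligatory and the optional sentence. State that surveys, visits and adverse-event follow-up continue to 12 months unless consent is withdrawn. Delete the reference to unblinding. When to stop treatment remains a clinical decision.

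**Cost.** A short wording amendment to the two sections, with the adverse-event log aligned if it repeats the old definition. It means slightly more adverse-event recording, with no new visits, surveys or staff.
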